3.3.3 Secondary Efficacy Endpoints

Secondary efficacy variables include the change from baseline values at each of the following scheduled post-baseline assessment time-points:

- total hemoglobin,
- free hemoglobin,
- haptoglobin,
- reticulocytes
- hemoglobinuria.

Additionally, achieving an LDH < 1.5×ULN will be a secondary efficacy endpoint (i.e., a dichotomous endpoint) which will be assessed during the primary evaluation period and at each the scheduled post-baseline assessment time-points.

3.3.4 Pharmacodynamic Endpoints

Pharmacodynamic endpoints include:

- Changes from baseline CH_{50}
- Changes from baseline in sRBC lysis for the classical complement pathway
- Changes from baseline in Wieslab ELISA for alternative complement pathway
- Changes from baseline in C5 concentration levels.

3.3.5 Pharmacokinetic Endpoints

Drug exposure will be evaluated using PK parameters derived from non-compartmental methods. All calculations for the final analysis will be based on actual sampling times. Individual PK parameters will be presented in listings and summarized using descriptive statistics.

Pharmacokinetic endpoints include:

- Plasma concentrations of RA101495 and its major metabolites
- Maximum plasma concentration (C_{max})
- Time corresponding to C_{max} (t_{max})
- Area under the drug concentration-time curves (AUC_{0-t})
- Plasma concentrations of eculizumab.

3.3.6 Quality of Life Assessments

Quality of life assessments will be performed according to the Time and Events Table (Table 2). The following QOL questionnaires will be used during this study:

- European Organization for the Research and Treatment of Cancer Quality of Life Questionnaire-C30 (EORTC-QLQ-C30)
- Functional Assessment of Chronic Illness Therapy-Fatigue (FACIT-Fatigue) Scale
- EuroQol-5D (EQ-5D).

3.3.6.1 EORTC-QLQ-C30

The EORTC QLQ-C30 consists of 30 questions, which are incorporated into 5 functional domains (physical, role, cognitive, emotional, and social domains; see Table 4); a global health status/global QOL scale; 3 symptom scales (fatigue, pain, and nausea and vomiting scales); 6 single items that assess additional symptoms (e.g. dyspnea, appetite loss, sleep disturbance, constipation, and diarrhea); and the

perceived financial burden of illness treatment (Aaronson, 1993; Aaronson, 1996). Subjects answer questions based on symptoms/status over the preceding week.

The QLQ-C30 is composed of both multi-item scales and single-item measures. These include five functional scales, three symptom scales, a global health status / QoL scale, and six single items.

Each of the multi-item scales includes a different set of items - no item occurs in more than one scale.

All of the scales and single-item measures range in score from 0 to 100. A high scale score represents a higher response level.

- a high score for a functional scale represents a high / healthy level of functioning
- a high score for the global health status / QoL represents a high QoL,
- a high score for a symptom scale / item represents a high level of symptomatology / problems.

The principle for scoring these scales is the same in all cases:

- 1) Estimate the average of the items that contribute to the scale; this is the raw score.
- 2) Use a linear transformation to standardize the raw score, so that scores range from 0 to 100; a higher score represents a higher ("better") level of functioning, or a higher ("worse") level of symptoms.

Table 4: Scoring the EORTC QLQ-C30

	Scale	Number of Items	Item Range*	Item Numbers	Functional scales
Global health status / QoL					
Global health status/QoL	QL2	2	6	29, 30	
Functional scales					
Physical functioning	PF2	5	3	1 to 5	F
Role functioning	RF2	2	3	6, 7	F
Emotional functioning	EF	4	3	21 to 24	F
Cognitive functioning	CF	2	3	20, 25	F
Social functioning	SF	2	3	26, 27	F
Symptom scales / items					
Fatigue	FA	3	3	10, 12, 18	
Nausea and vomiting	NV	2	3	14, 15	
Pain	PA	2	3	9, 19	
Dyspnoea	DY	1	3	8	
Insomnia	SL	1	3	11	
Appetite loss	AP	1	3	13	

Constipation	CO	1	3	16	
Diarrhoea	DI	1	3	17	
Financial difficulties	FI	1	3	28	
* Item range is the difference between the possible maximum and the minimum response to individual items; most items take values from 1 to 4, giving range = 3. The exceptions are the items contributing to the global health status/QoL, which are 7-point questions with range = 6,					

For all scales, the Raw Score is the mean of the component items.

For functional scales the score is:

$$\text{Score} = \{1 - (\text{Raw score} - 1)/(\text{range})\} \times 100$$

and for Symptom scales/items and Global health status/QoL:

$$\text{Score} = \{(\text{Raw score} - 1)/(\text{range})\} \times 100.$$

3.3.6.2 FACIT-Fatigue

The FACIT-Fatigue Scale is a 13-item, easy to administer tool that measures an individual’s level of fatigue during their usual daily activities over the preceding week. The level of fatigue is measured on a five point ordinal scale (4 = not at all fatigued to 0 = very much fatigued) [Webster, 2003].

The items and scoring algorithm are given in Table 5.

Table 5: FACIT Fatigue Scale Scoring

Item
I feel fatigued
I feel weak all over
I feel listless (“washed out”)
I feel tired
I have trouble starting things because I am tired
I have trouble finishing things because I am tired
I have energy
I am able to do my usual activities
I need to sleep during the day
I am too tired to eat
I need help doing my usual activities
I am frustrated by being too tired to do the things I want to do
I have to limit my social activity because I am tired

 • Item Response is the “raw score” on the 0 – 4 point scale (0: Not at all – 4: Very Much). • Overall Fatigue Subscale Score Algorithm: 
 ○ Sum the individual scores ○ Multiple the sum by 13 ○ Divide by the # of non-missing items answered

The higher the score, the better the QOL.

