3.1.4 Handling of Missing/Incomplete Values

Unless otherwise explicitly specified, missing data will not be imputed; observed cases will be used in the analyses.

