3.9.5.2 FACIT-Fatigue

The overall FACIT-Fatigue score and the individual 13 item scores (Section 3.3.6.2) will be summarized as well as the corresponding change from baseline scores for each scheduled assessment time-point. Shift tables displaying the individual item values from baseline to each post-baseline visit will also be presented.

The change from baseline for the FACIT-Fatigue overall and individual item scores will be assessed by a two-sided Wilcoxon signed-rank test.

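### The FACIT-Fatigue overall score is prorated with no minimum number of answered items, so a nearly blank form counts as a full score

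*SAP*

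**What the plan says.** SAP 3.3.6.2 introduces the instrument: "The FACIT-Fatigue Scale is a 13-item, easy to administer tool". Items are rated on a five-point scale, "4 = not at all fatigued to 0 = very much fatigued". Table 5 then gives three scoring steps: "Sum the individual scores"; "Multiple the sum by 13" (evidently 'multiply'); "Divide by the # of non-missing items answered". Nothing says how many items must be answered before the score is computed.

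SAP 3.9.5.2 takes the score into a test: "The change from baseline for the FACIT-Fatigue overall and individual item scores will be assessed by a two-sided Wilcoxon signed-rank test". The overall score is tabulated for the Safety and Per Protocol Populations.

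The general rule in SAP 3.1.4 is that "missing data will not be imputed; observed cases will be used in the analyses", but the same sentence exempts anything the plan specifies explicitly. There is no completeness requirement in that section, in the population definitions (SAP 3.2), in SAP 3.9.5.2, in protocol 11.6.1.2, or in the post-lock amendment to the SAP.

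The questionnaire is given on Day 1 and at Weeks 4, 8 and 12, and not at Screening (protocol Table 1, SAP Table 2).

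**The concern.** Prorating a scale is reasonable when a few items are missing. Without a floor, the same formula also turns one or two answers into a total on the full scale, and nothing later in the plan marks that total as less reliable. Each subject contributes one unweighted change score. The signed-rank test ranks changes by size, so a coarse total from a sparse form can take a higher rank than the changes from complete forms.

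With 6 to 8 subjects, a single form of this kind can shift the group mean and the p-value. Day 1 is the most exposed visit. Under SAP 3.1.3 a sparse Day 1 form would count as a non-missing baseline. Its error would pass into all three post-baseline changes, and no Screening form exists to fall back on.

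**Working it through.** **The plan's own figure.** The documents give no precision figure for FACIT-Fatigue. Their only design figure is the standard error for LDH change (SAP 3.11). It reproduces, sqrt(2 × 443² × (1 − 0.8) / 6) = 114.4 U/L against about 114 stated, but it has no bearing on this point.

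**Inputs from the documents.** 13 items, each scored 0 to 4 (SAP 3.3.6.2), so a complete form totals 0 to 13 × 4 = 52. Score = sum × 13 / k, where k is the number of items answered (Table 5). Planned enrolment is 6 to 8 (SAP 2.2.1).

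**Assumptions, not from the documents.** A within-person item SD, S, of 1.0, with a range of 0.7 to 1.3, and unanswered items that are a random subset of the 13.

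**Step 1: one answered item.** With k = 1 the score is s × 13 / 1 for s = 0 to 4, that is 0, 13, 26, 39 or 52. One response category moves the total by 13 points, against 1 point on a complete form.

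**Step 2: largest possible error.** The gap between the prorated total and the true total is at most 4 × (13 − k): 48 points at k = 1, 24 at k = 7, and 0 at k = 13.

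**Step 3: typical error.** The error SD of the prorated total is 13 × S × sqrt((1/k) × (1 − k/13)). Dividing by 6 gives the contribution of one such form to the mean of six subjects.

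| Items answered (k) | Error SD, S = 1.0 | S = 0.7 to 1.3 | On the mean, n = 6, S = 1.0 |
|---|---|---|---|
| 1 | 12.5 | 8.7 to 16.2 | 2.1 |
| 3 | 6.6 | 4.6 to 8.6 | 1.1 |
| 6 | 3.9 | 2.7 to 5.1 | 0.6 |
| 7 | 3.3 | 2.3 to 4.3 | 0.6 |
| 11 | 1.5 | 1.1 to 2.0 | 0.3 |
| 13 | 0 | 0 | 0 |

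**Step 4: effect on the test (hypothetical).** Five complete forms with changes +2, +3, +5, +6 and +7 give an exact two-sided signed-rank p of 2/32 = 0.0625. Add a sixth subject who scored 2 on every item at baseline (total 26).

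- At follow-up the subject answers one item, one category lower. The prorated total is 13 and the change is −13, which takes the top rank, so p = 28/64 = 0.4375.
- Had the other twelve items been answered and unchanged, the total would be 25 and the change −1, which takes the lowest rank, so p = 4/64 = 0.0625.
- If the single item is one category higher, the change is +13 and p = 2/64 = 0.031.

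The same single-category drop gives p = 0.4375 or 0.0625, depending only on whether the other twelve items were left blank.

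The direction of item coding differs between the text of SAP 3.3.6.2 and Table 5. That is a separate matter and does not affect this arithmetic.

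**The case against.** The best case against the point is that it is unlikely to matter. FACIT-Fatigue is exploratory and scheduled at four clinic visits, and nothing in the documents suggests that near-blank forms are expected. The large figures need a form with one answer. With 11 of 13 answered, the error on a six-subject mean is about 0.3 points, and a floor would leave that form as it is. A sparse form would also be visible, because items are summarised individually with shift tables and listed by subject. QLQ-C30 has its own fatigue scale too. All of this stands and limits the point to a minor one. But visibility in a listing does not keep the score out of the test.

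Two stronger readings are tempting, and the documents do not support either.

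- A reader might infer that Table 5 breaks the SAP's rule against imputation. It does not: SAP 3.1.4 allows explicitly specified exceptions, and Table 5 is one. What is missing is a floor.
- A reader might infer that QLQ-C30 follows the opposite rule and loses a whole scale when one item is missing. SAP 3.3.6.1 says only: "For all scales, the Raw Score is the mean of the component items". That could mean the answered items or all items, and the observed-cases wording in SAP 3.1.4 does not settle it. The handling is simply not stated.

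There is also a question of version. The post-lock amendment cites SAP Version 3.0 of 22 March 2018. Its table list includes total bilirubin tables that it does not mark as new, and the SAP's own list lacks them. The SAP text available may therefore predate Version 3.0, and Table 5 should be checked against the final version.

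**Conclusion.** The point holds as a minor one. The plan states a scoring rule that gives an unreliable total for a sparse form and treats that total like any other. The size depends on the assumed item SD and on random missingness. Items skipped for a reason would add bias that these figures do not include. If every form is complete the effect is zero, and the proposed floor alters results only if some form has six or fewer answers. The documents give no completion data, so whether this happened cannot be judged from them. The primary and secondary endpoints are not affected.

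**What to change.** Add one sentence to SAP Table 5: compute the prorated overall score only when more than half of the items (at least 7 of 13) are answered, and otherwise set it to missing at that visit. The threshold is a proposal and is not taken from the documents. The error falls gradually with k (3.9 at six items, 3.3 at seven), so the exact cut-off matters less than having one. Relative to a one-item form, a seven-item minimum cuts the error SD by 1 − 3.3/12.5, about 73%.

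The SAP amendment describes itself as written after database lock. If scoring has already been run, report the number of answered items per form. If any form falls below the floor, show the overall-score results with and without it, labelled post hoc as SAP section 1 requires for analyses not specified in advance.

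The cost is one sentence. The downside is that a mostly blank form gives no overall score at that visit, and a mostly blank Day 1 form leaves that subject with no overall change score at all. Item-level summaries would still use the answers given.

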2.2.5 Exploratory Assessments

Exploratory endpoints include:

- Changes from baseline in QOL questionnaires

- European Organization for Research and Treatment of Cancer-Quality of Life Questionnaire (EORTC QLQ-C30)
- Functional Assessment of Chronic Illness Therapy-Fatigue Scale (FACIT-Fatigue)
- EuroQol 5D (EQ-5D)
- Treatment satisfaction questionnaire

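### SAP Table 5 sums unreversed FACIT-Fatigue responses yet calls a higher total better, so broad improvement in fatigue would be read as worsening

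*SAP*

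**What the plan says.** SAP 3.3.6.2 refers the reader to Table 5 for both the items and the scoring algorithm. Table 5 lists 13 items. Its footnote defines the item response as the raw score on a "0 – 4 point scale (0: Not at all – 4: Very Much") coding, with no distinction between items. The algorithm is then "Sum the individual scores", multiply by 13, and divide by the number of items answered. The section closes with "The higher the score, the better the QOL".

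The opening sentences of the same section, and protocol 11.6.1.2, describe the scale the other way round: "4 = not at all fatigued to 0 = very much fatigued". Neither place gives a rule for getting from a response to a score.

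SAP 3.9.5.2 uses the result widely: "The change from baseline for the FACIT-Fatigue overall and individual item scores will be assessed by a two-sided Wilcoxon signed-rank test". It also asks for summaries of the overall and item scores and for item shift tables. The SAP table list has six FACIT tables, covering the Safety and Per Protocol Populations.

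**The concern.** Eleven of the listed items are negatively worded, so agreeing more strongly means more fatigue. Two are positively worded: the item on having energy and the item on being able to do usual activities. A plain sum of responses coded 0 to 4 in the direction of agreement therefore rises as fatigue worsens, which contradicts the stated interpretation.

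Reversal is not something this SAP leaves to convention. For the EORTC QLQ-C30, section 3.3.6.1 prints a separate formula after "For functional scales the score is", and that formula subtracts from 1 so that a high score means good functioning. Nothing comparable is written for FACIT-Fatigue in SAP 3.3.6.2, SAP 3.9.5.2 or protocol 11.6.1.2.

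At stake is the direction of a patient-reported fatigue result. Because the two positive items pull against the other eleven, the error is also more than a change of sign: subjects can be scored in opposite directions, which changes ranks and p-values.

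**Working it through.** **Inputs.** All come from SAP 3.3.6.2 and Table 5: 13 items, of which 11 are negative and 2 positive by their wording; responses r from 0 to 4; proration 13/m, where m is the number of items answered. The SAP states no score range, so there is no figure of the plan's own to reproduce.

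**Three scoring rules that the text could support**

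- Table 5 as written: total = (sum of r) × 13/m.
- Oriented: item score = 4 − r for the 11 negative items and r for the 2 positive items; total = sum × 13/m.
- Lead-in anchors used as response codes for every item: total = (sum of 4 − r) × 13/m.

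**Change formulas, complete data.** Let N and P be the summed improvement, in categories, on the negative and positive items. The change in total is −N + P under Table 5, N + P when oriented, and N − P under the lead-in anchors.

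| Pattern | Table 5 as written | Oriented | Lead-in anchors as codes |
|---|---|---|---|
| Least fatigued (negative items 0, positive items 4) | 2×4 = 8 | 13×4 = 52 | 11×4 = 44 |
| Most fatigued (negative items 4, positive items 0) | 11×4 = 44 | 0 | 2×4 = 8 |
| One-category improvement, all 13 items (N = 11, P = 2) | −9 | +13 | +9 |
| Same, 11 negative items only | −11 | +11 | +11 |
| Same, 2 positive items only | +2 | +2 | −2 |

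Table 5 as written reverses the scale for broad change. The lead-in anchors get the broad direction right but count the two positive items backwards.

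**Missing items.** Take the least-fatigued subject under Table 5 as written. With complete data the total is 8. With one positive item skipped it is 4 × 13/12 = 4.3, and with one negative item skipped it is 8 × 13/12 = 8.7. The oriented score is 52 in all three cases (48 × 13/12 = 52 when one item is skipped). Without reversal, proration therefore depends on which item was skipped.

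**Effect on the test.** If every subject changes in the same direction, the exact two-sided signed-rank p is 2/2^n: 2/64 = 0.031 for n = 6 and 2/256 = 0.008 for n = 8. It is the same for either sign.

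**Mixed change, with assumed data (n = 6).** Take N = 5, 4, 3, 2, 1, 6 and P = 1, 2, 0, 3, 2, 1.

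- Oriented changes: 6, 6, 3, 5, 3, 7. The median is +5.5 and p = 2/64 = 0.031.
- Table 5 as written: −4, −2, −3, +1, +1, −5. The median is −2.5. The ranks of the absolute values are 1.5, 1.5, 3, 4, 5, 6, and the positive rank sum is 3. Five of the 64 sign patterns give a sum of 3 or less, so p = 10/64 = 0.156.

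**The case against.** Five points can be made on the other side.

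- **The lead-in can be read as describing item scores that are already oriented.** On that reading the total is right and agrees with the closing statement. However, Table 5, which the section names as the algorithm, defines the item response as the raw score in the opposite coding, and no conversion is given. The section contradicts itself, and following its named algorithm literally gives the wrong direction.
- **The SAP text may not be the version in force at lock.** It cites protocol version 1.1 of 20 October 2016, while the post-lock amendment refers to SAP Version 3.0 of 22 March 2018 and carries a different table list. Version 3.0 could have corrected the rule, and the documents cannot settle this. The amendment does keep all six FACIT tables and mentions no scoring change.
- **A scoring column could have been lost from Table 5 when the PDF was read.** This cannot be excluded, and the source file should be checked. SAP Tables 4 and 6 kept their columns, so nothing points to a loss.
- **The consequence is limited.** The SAP lists the quality-of-life questionnaires under "Exploratory endpoints include", the study plans 6 to 8 subjects, a separate EORTC fatigue scale is scored, and item shift tables might expose a total that moves against its items. This stands, and it keeps the point well below anything touching the primary analysis. The p-value difference above also rests on assumed data in which two of the six subjects improve more on the two positive items than on the eleven negative ones.
- **The database is already locked.** This stands as well. It changes the practical remedy from guiding the programming to verifying it.

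**Conclusion.** The concern holds. As written, the Table 5 rule and the stated interpretation cannot both be right. Following them together turns a uniform one-category improvement, +13 when oriented, into −9, and reports it as worsening. This rests only on the wording of the items and on Table 5 being complete in the copy read; no outside scoring manual is needed. The error matters only if the program follows Table 5 literally, and the documents do not show whether it did. A programmer who knows the instrument may have reversed the items. The point should be fixed, but its reach is the exploratory FACIT-Fatigue outputs. The LDH primary endpoint and the other efficacy analyses are not affected.

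**What to change.** In Table 5, keep the response coding from 0 (not at all) to 4 (very much) and add the missing step:

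- Item score = 4 − response for the 11 negatively worded items.
- Item score = response for the energy item and the able-to-do-usual-activities item.
- Total = sum of item scores × 13 / items answered, range 0 to 52, higher meaning less fatigue.

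Describe the lead-in anchors as the oriented item score, so that the SAP stays consistent with protocol 11.6.1.2. State in SAP 3.9.5.2 and in the table shells whether item summaries, item tests and shift tables show raw responses or oriented scores.

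Because the database is locked, first check the source PDF, SAP Version 3.0 and the program against this rule. Record the rule used in the clinical study report, and re-run the FACIT outputs if it was not followed. The cost is a few lines of SAP text and code and one program check, with no new data.

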3.3.6.3 EQ-5D

The EQ-5D 3 level version [EuroQol, 1990] is a standardized instrument for measuring generic health status. The EQ-5D consists of the EQ-5D descriptive system and the EQ visual analogue scale (VAS). The EQ-5D descriptive system comprises the following five dimensions: mobility, self-care, usual activities, pain/discomfort and anxiety/depression; each dimension has three levels:

- Level 1: indicating no problem
- Level 2: indicating some problems
- Level 3: indicating extreme problems.

For the EQ-5D visual analog scale (VAS) question the patient rates how good or bad their health is today on a 0 – 100 point scale (0 representing worst imaginable health state and 100 representing best imaginable health state).

3.3.6.4 Treatment Satisfaction Questionnaires

The following treatment satisfaction questionnaire will be administered to subjects to assess overall satisfaction with SC administration of the study medication at the end of the 12-week Treatment Period.

“How satisfied are you with the overall method of study medication administration (subcutaneous self-injection)?”

The following more targeted questionnaire will be administered to assess preference for daily SC self-injection at home compared with biweekly infusions given by a health-care professional in the clinic.

“Overall how satisfied are you with the method of medication administration used in this study (daily subcutaneous self-injection) compared with intravenous eculizumab infusions every 2 weeks?”

Both questions will use the following 5-point Likert response scale:

- Very Dissatisfied=1
- Dissatisfied=2
- Neutral=3
- Satisfied= 4

- Very Satisfied= 5.

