6.4 DEVELOPMENT RATIONALE

RA101495 is being developed to treat patients with PNH. Based on PK and PD data generated to date, RA101495 has the potential to provide several advantages over the only currently approved therapy for PNH, eculizumab.

Daily administration of RA101495 is expected to result in near complete and sustained suppression of C5 for improved control of hemolysis. Continuous inhibition of hemolysis is important in the prevention of breakthrough hemolysis. Eculizumab at the approved dose of 900 mg biweekly has been associated with breakthrough hemolysis in some patients requiring dose increases beyond the approved dose described in the current product label [Hill, 2005]. Breakthrough hemolysis with eculizumab treatment typically occurs towards the end the biweekly infusion cycle and has been shown to be associated with sub-therapeutic eculizumab levels at those time points [Nakayama, 2016; Brodsky, 2014]. Daily dosing with RA101495 is designed to ensure that C5 is continuously inhibited and is therefore expected to eliminate end-of-cycle breakthrough episodes.

As a self-administered SC product, RA101495 has the potential to improve treatment satisfaction and improve dosing convenience for patients with PNH, and may enable a reduction in the cost of providing care. The current standard-of-care requires health professionals to administer eculizumab via a biweekly intravenous (IV) infusion. Published studies of patient preferences for SC versus IV therapy show a clear preference for SC administration, and SC administration has been shown to increase compliance, patient satisfaction and QOL, as well as reduce treatment costs, drug requirements, and the complications of intravenous access [Stoner, 2015; Besarab, 2002]. Phase 2 studies of RA101495 will include quantitative instruments for evaluating QOL.

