11.6.2 TREATMENT SATISFACTION QUESTIONNAIRE

A treatment satisfaction questionnaire using a 5-point Likert response scale will be administered to all subjects to assess overall satisfaction with SC administration of the study medication and to assess their preference for daily SC self-injection at home compared with biweekly infusions given by a health-care professional in the clinic.

The questionnaire will be completed at the end of the 12-week Treatment Period.

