3.9.5.4 Treatment Satisfaction Questionnaires

For both treatment satisfaction questions (Section 3.3.6.4) the number and percentage for each response category will be summarized.

Both treatment satisfaction will be assessed by a two-sided Wilcoxon signed-rank test testing against a score of neutral. This is equivalent to subtracting 3 from each of the scores and testing against a score of 0 (i.e., the default for a Wilcoxon signed-rank test).

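### The item meant to measure preference for daily SC self-injection over IV infusions has absolute satisfaction options, so its test against Neutral cannot establish a preference

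*SAP*

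**What the plan says.** Protocol 11.6.2 gives the questionnaire two purposes: overall satisfaction with SC administration, and to "assess their preference for daily SC self-injection at home compared with biweekly infusions given by a health-care professional in the clinic". It is completed once, at the end of the 12 weeks of treatment.

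SAP 3.3.6.4 turns this into two items. The first asks about satisfaction with SC self-injection and names no comparator. The second is introduced thus: "The following more targeted questionnaire will be administered to assess preference for daily SC self-injection at home compared with biweekly infusions". Its stem asks "how satisfied are you with the method of medication administration used in this study (daily subcutaneous self-injection) compared with intravenous eculizumab infusions" every 2 weeks.

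On the answers, the SAP says "Both questions will use the following 5-point Likert response scale". The options are *Very Dissatisfied* = 1, *Dissatisfied* = 2, *Neutral* = 3, *Satisfied* = 4 and *Very Satisfied* = 5.

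On the analysis, SAP 3.9.5.4 plans counts and percentages per response category and adds: "Both treatment satisfaction will be assessed by a two-sided Wilcoxon signed-rank test testing against a score of neutral". It explains that this means subtracting 3 from each score and testing against 0.

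**The concern.** The second item is meant to measure a choice between two routes. Its stem is comparative, but its answers are levels of satisfaction and none of them mentions IV infusion or preference. For 3 to work as the null value for preference, every subject without a preference would have to tick *Neutral*. Neither document defines *Neutral* that way or tells subjects how to answer if they are equally content with both routes.

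A subject equally content with SC and IV can therefore truthfully tick *Satisfied*. So can one who finds SC acceptable but would choose the infusion, if that subject gives little weight to the comparison. A score above 3 may reflect contentment with SC, preference for SC, or both, and no other item separates the two.

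At stake is whether the study can say anything about patients' preference for self-injection. A small p-value from this item could be read as evidence of preference, which the item cannot supply.

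**Working it through.** The documents give no figure for this item, so there is none to reproduce. (The one numerical design figure, the LDH standard error of about 114 U/L, does reproduce: 443 × √(2 × (1 − 0.8)) / √6 = 114.4. It has no bearing here.)

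**Inputs from the documents.** Planned enrolment is about 6–8 subjects (SAP 2.2.1). The scores are 1 to 5 with *Neutral* = 3 (SAP 3.3.6.4). The test is a two-sided Wilcoxon signed-rank test on score − 3 (SAP 3.9.5.4).

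**Assumptions.** The significance level is taken as 0.05, because neither document states one. The p-value is taken as exact, with *Neutral* answers (zeros) dropped and mid-ranks for ties, because the SAP does not specify this.

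**Step 1: smallest attainable p.** If all m non-neutral answers lie on one side of 3, only the all-positive and all-negative sign patterns are as extreme as the data. So p = 2/2^m:

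- m = 5: 2/32 = 0.0625
- m = 6: 2/64 = 0.0313
- m = 7: 2/128 = 0.0156
- m = 8: 2/256 = 0.0078

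Five or fewer non-neutral answers cannot give p < 0.05.

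**Step 2: the extreme case.** If every subject ticks *Satisfied*, all differences are +1. Then p = 0.031 at n = 6 and 0.008 at n = 8, whether or not anyone prefers SC.

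**Step 3: how far from the extreme the result survives.** At n = 6, five *Satisfied* and one *Neutral* give p = 0.0625. Five *Very Satisfied* and one *Dissatisfied* also give 0.0625. So all six answers must lie on the same side of *Neutral*. At n = 8, six *Satisfied* and two *Neutral* give 0.0313, while seven *Satisfied* and one *Dissatisfied* give 0.0703.

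**Step 4: a range.** Suppose that no subject has a preference and that every subject answers on absolute satisfaction, disregarding the comparison in the stem. The probability of p < 0.05 then depends on an assumed distribution over scores 1–5. At n = 6 it is the share above *Neutral* raised to the sixth power, for example 0.8^6 = 0.26. The n = 8 values come from enumerating all response patterns.

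| Assumed distribution, scores 1–5 | Share above Neutral | n = 6 | n = 8 |
|---|---|---|---|
| .05/.10/.25/.40/.20 | 60% | 0.05 | 0.17 |
| 0/.05/.15/.50/.30 | 80% | 0.26 | 0.63 |
| 0/.03/.07/.50/.40 | 90% | 0.53 | 0.85 |

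These are upper-end figures, because they let nobody use the comparison.

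**Step 5: the same test on a comparative scale.** With no preference as the midpoint, indifferent subjects should spread symmetrically around 3. Under .05/.15/.60/.15/.05 and .10/.20/.40/.20/.10 (both assumed), the test rejects in either direction with probability 0.0001 to 0.0015 at n = 6 and 0.0014 to 0.0085 at n = 8. The problem lies in the answer options, not in the signed-rank test.

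**The case against.** The best defence is that the stem is explicitly comparative and is listed after an item that is not. Read in that order, *Neutral* can naturally mean no difference and *Dissatisfied* can mean worse than the infusion. A subject who would choose IV ticks *Satisfied* only by setting the comparison aside. The form as subjects saw it, and any instructions with it, are not in the documents.

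SAP 3.9.5.4 also speaks of satisfaction, not preference, and the output tables are titled as treatment satisfaction. With 6–8 subjects, the category counts and individual listings let a reader see every answer. The all-*Satisfied* case is extreme, and at n = 6 a single *Neutral* answer removes significance at 0.05.

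All of this stands and limits the size of the point. The amount of distortion depends on how subjects read the item, which is unknown. But the defence shows only that the score may carry some information on preference. It does not show that 3 marks its absence, and both documents name preference as the purpose of the item.

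**Conclusion.** The point holds as a limited one. A result above *Neutral* on the second item shows at most that subjects were satisfied with SC self-injection, and it does not establish that they prefer it to IV infusions. Following the plan exactly, p can reach 0.031 (n = 6) or 0.008 (n = 8) from subjects who are merely content with SC. This rests on an exact test, an assumed 0.05 level and at least six non-neutral answers. It affects one exploratory item; nothing on LDH or safety depends on it.

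A reader might infer more, but the documents do not support it:

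- **That the sponsor plans to claim a preference from this p-value.** No passage says so.
- **That the item is biased in the sponsor's favour.** That requires indifferent subjects both to disregard the comparison and to be content with SC. Neither is shown.
- **That the result would be a preference for RA101495.** The item concerns the method of administration, not the drug.
- **That the first item fails too, for want of a rating of IV eculizumab before the switch.** Protocol 6.4 says that "RA101495 has the potential to improve treatment satisfaction and improve dosing convenience for patients with PNH", but this is development rationale. Protocol 11.6.2 promises no change from baseline. The first item's test against *Neutral* may stand as a statement about satisfaction with SC only.

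**What to change.** Before data collection, or in any later study that reuses the item, give the second question a balanced comparative scale: strongly prefer IV every 2 weeks / prefer IV / no preference / prefer daily SC / strongly prefer daily SC. Make *no preference* the null value. The cost is new answer options on one question.

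For this study the SAP package contains an amendment written after database lock. Its summary of changes does not mention this item, and its table list keeps the treatment satisfaction tables unmarked. The remaining course is therefore to report the second item as satisfaction with SC using the counts and percentages already planned, drop its test against 3, and make no preference statement. This needs only SAP and report wording, and it fits Protocol 13.3.1, which plans descriptive summaries.

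The downside is that a favourable p-value on an exploratory item may be lost. A Day 1 rating of IV eculizumab on the same scale would allow a within-subject comparison in a later study, but it is an optional addition and not part of the correction.
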